The United States is experiencing an epidemic of opioid-related overdose deaths. Office-based buprenorphine treatment could expand access to treatment to the many opioid users who are not in treatment and who are at great risk for opioid overdose. However, office-based buprenorphine has two limitations that we will address in this application: 1) Patients prescribed buprenorphine by office-based providers can divert the buprenorphine for illicit use. 2) Many people in need of buprenorphine treatment do not initiate and remain in office-based buprenorphine treatment. We will use Video DOT and incentives to enhance office-based buprenorphine treatment. Video DOT is an innovative, mobile health platform that patients can use to record and submit videos of themselves taking medication that are then viewable on a secure, web portal for providers to confirm medication adherence. Video DOT could facilitate adherence to buprenorphine treatment and safeguard against diversion. The addition of incentives could engage out-of-treatment opioid users into treatment and increase treatment retention. Incentive interventions, which provide incentives to patients when they meet therapeutic goals, have been highly effective in promoting a wide range of health behaviors and have firm theoretical and empirical foundations. Incentive interventions can promote treatment engagement in individuals with substance use disorders, including out-of-treatment opioid users. We propose to develop and pilot test a novel combination of Video DOT and incentives to promote buprenorphine treatment engagement and adherence in out-of-treatment opioid users. The Video DOT+ intervention will provide an incentive for linking to buprenorphine treatment and facilitate retention in treatment by providing incentives for maintaining daily buprenorphine use as verified by the Video DOT system. The incentives will be integrated into the Video DOT platform and delivered remotely to reloadable credit cards to allow for the entire intervention to be delivered via mobile technology and to facilitate easy dissemination of the Video DOT+ system. Two randomized pilot studies are planned over 3 years. In both studies, out-of-treatment opioid users (N=105) will be referred to buprenorphine treatment and randomly assigned to a Usual Care (Control) group or Video DOT+ group. Video DOT+ participants will receive the Video DOT+ intervention being developed and evaluated in this project. We will assess participants every 4 weeks throughout a 24-week intervention period and at 12 weeks after the intervention ends. The primary outcome measure will be buprenorphine treatment adherence during the 24-week intervention. Secondary measures will include buprenorphine treatment engagement (linkage and retention), opioid use, risk of opioid overdose, and post-intervention effects. The project will allow for the development and preliminary evaluation of a novel intervention to promote buprenorphine treatment engagement and adherence in out-of-treatment opioid users.

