Two randomized pilot studies are planned over 3 years. In both studies, out-of-treatment opioid users will be recruited through street outreach, at agencies that serve the target population (e.g., The Baltimore City Health Department), word-of-mouth referrals, and by posting fliers and information sheets with our toll-free number in Baltimore publications (e.g., the city paper) -- methods that we have used previously to recruit out-of-treatment opioid users. Participants in Study 1 will be referred to buprenorphine treatment and randomly assigned to a Usual Care (Control) group or a Video DOT+ group. Participants in Study 2 will be invited to participate in a 7-day induction period, and then randomly assigned to a Usual Care (Control) group or a Video DOT+ group. Video DOT+ participants will receive the Video DOT+ intervention being developed and evaluated in this project. We will assess participants every 4 weeks throughout a 24-week intervention period and at 12 weeks after the intervention ends. The long-term goal of this line of research is to develop and disseminate a sustainable and scalable intervention that can promote buprenorphine treatment engagement and adherence, and thereby combat the opioid overdose epidemic.

4. Study Procedures

- a. Study design, including the sequence and timing of study procedures
(distinguish research procedures from those that are part of routine care).

STUDY 1 AND STUDY 2

Study Participants

Recruitment and screening. We will use the following recruitment procedures that we used successfully in our prior study with out-of-treatment opioid users ([name] et al., 2014): 1) We will inform

Date: February 11, 2020

Principal Investigator: [name]

Application Number: IRB00186156

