Concomitant Medications: Consistent with standard clinical practice treatment, some medications will be available to participants as needed during the supervised buprenorphine induction and at discharge from the induction. The following medications may be offered during the supervised buprenorphine induction: acetaminophen (500mg, 1-2 tablets every 6 hours as needed for pain), clonidine (0.1-0.2mg every 4 hours as needed), dicyclomine (10mg every 6 hours as needed for abdominal cramps), hydroxyzine (25mg, 1-2 tablets every 8 hours as needed for anxiety), ibuprofen (600mg every 6 hours as needed for myalgia), loperamide (2mg, 1-2 tablets every 4 hours as needed for diarrhea), methocarbamol (750mg, 1 tablet every 4 hours as needed for myalgia), and ondansetron (8mg every 6 hours as needed for nausea/vomiting). The following medications may be offered at discharge from the induction: clonidine (up to four 0.1mg tablets, 1 tablet to be taken every 6 hours as needed), hydroxyzine (25mg, 1-2 tablets as needed for anxiety), ibuprofen (up to four 600mg tablets, 1 tablet to be taken every 6 hours as needed for myalgia), ondansetron (8mg, 1 tablet as needed for nausea/vomiting), and trazodone (100mg, 1 tablet as needed for sleep). These concomitant medications will be available to reduce withdrawal symptom severity during the buprenorphine induction and at time of discharge from the supervised induction.

Concomitant medications will be administered as needed per clinical recommendation and overseen by the study clinician co-investigator(s) who are conducting the supervised buprenorphine induction. Not all medications will be dispensed. The provision of these additional supportive medications may be necessary to prevent treatment attrition.

- b. Justification and safety information if FDA approved drugs will be administered for non-FDA approved indications or if doses or routes of administration or participant populations are changed.

N/A

- c. Justification and safety information if non-FDA approved drugs without an IND will be administered.

N/A

7. Study Statistics

Separate statistical analyses will be conducted for Study 1 and Study 2. We will compare the Usual Care Control and Video DOT+ groups on primary and secondary outcome measures. To preserve statistical power and minimize the likelihood of endorsing false conclusions, we identified one primary outcome measure and several secondary outcome measures, each associated with a *Specific Aim*.

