We used Liu and Liang (1997) to determine the number of participants required to detect a difference between groups with 80% power. The adjacent figure shows the total number of participants (N) that would be required to detect a difference of 25% between the Usual Care Control and Video DOT+ groups with the six assessments during the 24-week intervention period. The figure shows different percentages for the Usual Care Control group because that value affects the sample size required. Twenty-five percent is smaller than the increase produced in our prior study of incentives to promote daily adherence to oral naltrexone in opioid-dependent adults (Dunn et al., 2013). It is also smaller than the incentive effects in promoting drug abstinence, medication adherence, and other health behaviors as shown in three different meta-analyses (Petry et al., 2012; Prendergast et al. 2006; Lussier et al., 2006). Based on this, we need to randomize 64 participants (horizontal dashed line) to detect a difference between the Usual Care Control and the Video DOT+ groups on the primary outcome measure.

d. Early stopping rules.

The PI ([name], PhD) and two co-investigators at Johns Hopkins University School of Medicine ([name], PhD; [name], MD) will provide data and safety monitoring of the proposed studies. To monitor adverse events, all staff members who have regular contact with study participants are instructed on the need to report to an investigator any indication that an adverse event has occurred. When

Date: February 11, 2020

Principal Investigator: [name]

Application Number: IRB00186156

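### The planned N=105 is not assigned to either of two separately tested studies; if it is their combined total, at least one study falls below the 64 behind the 80% power statement.

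*Combined protocol and SAP*

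**What the plan says.** The abstract announces the programme with "Two randomized pilot studies are planned over 3 years". Its next sentence gives the only planned size in the documents: "In both studies, out-of-treatment opioid users (N=105) will be referred to buprenorphine treatment and randomly assigned to a Usual Care (Control) group"; the other arm is Video DOT+. The sentence gives no split and does not mark 105 as a total or as a number per study.

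Section 7 (Study Statistics) says "Separate statistical analyses will be conducted for Study 1 and Study 2", and section 7c repeats this. Section 7a gives both studies the same primary outcome, buprenorphine-positive urine at the 4-week assessments. Tests are two-sided at 0.05.

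The Power Analyses part of section 7c gives the only power-based number: "we need to randomize 64 participants (horizontal dashed line) to detect a difference between the Usual Care Control and the Video DOT+ groups". It names no study. The number is a total over both arms: "The adjacent figure shows the total number of participants (N) that would be required to detect a difference of 25" (percent). The control rates are said to be in the figure: "The figure shows different percentages for the Usual Care Control group because that value affects the sample size required".

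In section 4, the Experimental Design text of each study limits stratification because of that study's proposed sample size, but no size is attached to either study.

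**The concern.** The numbers 105 and 64 each appear once. Neither is assigned to a study, and nothing links them. Because the studies are tested separately, the power that matters is the power within each study at its own number randomized. The 80% statement stands in a section written for both, so a reader will take it to cover both. If 105 is shared between them, it cannot: two studies of 64 would need 128.

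Two things depend on this. First, a null result in either study has to be read against that study's planned power, which the documents do not give. Second, the plan defends its target effect with "Twenty-five percent is smaller than the increase produced in our prior study of incentives to promote daily adherence to oral naltrexone". That defence is made for 25 points. A smaller study needs a larger difference for the same power, so the detectable difference should be restated for it.

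**Working it through.** **Inputs from the documents.** Planned size 105 (abstract). Required size 64, both arms together, with 80% power, a difference of 25% read as percentage points, and six assessments (section 7c, Power Analyses). Two-sided alpha 0.05 (section 7c, Statistical Analyses). Two studies, analysed separately (section 7). The control rates are in a figure not reproduced in the text available here. The text gives no within-person correlation.

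**1. Can 64 be reproduced?** Not exactly, because it depends on those two missing values. For a repeated binary outcome with constant correlation ρ and 1:1 allocation (assumed):

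n per arm = (1.960 + 0.842)² × [p₁(1−p₁) + p₂(1−p₂)] / 0.25² × (1 + 5ρ)/6

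This gives a total of 64 at ρ of about 0.45 for control rates of 35% to 40%, about 0.50 at 25% or 50%, about 0.55 at 20%, and about 0.76 at 10%. So 64 is plausible. It is taken as given below.

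**2. What the readings imply.**
- 105 is the total. Two studies of 64 would need 2 × 64 = 128, more than 105, so at least one study is below 64. If one has 64, the other has 105 − 64 = 41. An even split gives 52 and 53.
- 105 is per study. Each exceeds 64.

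**3. Power for 25 points if 64 gives exactly 80% at the true control rate.** Control rate and correlation then cancel:

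power(N) = Φ(√(N/64) × (1.960 + 0.842) − 1.960)

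| N in a study | √(N/64) | Power |
|---|---|---|
| 41 | 0.800 | 61.1% |
| 52 | 0.901 | 71.4% |
| 53 | 0.910 | 72.2% |
| 64 | 1.000 | 80.0% |
| 105 | 1.281 | 94.8% |

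**4. Power if 64 is instead the worst case over control rates.** The plan draws one horizontal line at 64 on a figure in which the control rate varies, so 64 may be the most demanding case. Let V(p) = p(1−p) + (p+0.25)(0.75−p), with unpooled variance and the same correlation at every rate. V is largest at p = 0.375, where V = 0.46875. At p = 0.10, V = 0.3175, so the required N is 64 × 0.3175/0.46875 = 43.3. Replace N/64 in step 3 by (N/64) × 0.46875/V(p):

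| N in a study | Control 37.5% (lowest power) | Control 10% (highest power in 10–50%) |
|---|---|---|
| 41 | 61% | 78% |
| 52 | 71% | 87% |
| 53 | 72% | 87% |

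On this assumption the values in step 3 are the bottom of the range. At a 10% control rate a study of 52 or 53 would exceed 80%; a study of 41 stays below 80% throughout.

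**5. Detectable difference at 80% power.** With the anchor of step 3 and variance held fixed, it is 25 × √(64/N): 31.2 points at 41, 27.7 at 52, 27.5 at 53 and 19.5 at 105. Letting the variance change with the difference, over control rates of 10% to 50%, gives 30.2 to 32.0 at 41, 27.1 to 28.1 at 52–53 and 18.8 to 20.0 at 105.

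**The case against.** The strongest reply is that no contradiction has been proved. A reader might infer that the plan is 23 participants short (128 − 105). That needs two premises the documents do not state: that 105 is the combined total, and that 64 is required in each study.

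- Against the first premise, The Proposed Plan in section 3 opens a sentence with "In both studies, out-of-treatment opioid users will be recruited through street outreach", where the phrase means each study. Read the same way in the abstract, 105 is per study and exceeds 64.
- Against the second, 64 + 41 = 105 exactly. If 64 was meant for one study only, no stated requirement is missed.

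Both points stand, so the shortfall of 23 is not a finding. Neither fully settles the matter. No passage states a 64 + 41 split, and under it a separately tested study of 41 has no power statement of its own. With 105 per study, the plan does not explain why it randomizes 41 more than it says it needs.

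The missing figure also limits what can be said. It may carry a study label or the correlation, and the plan says it carries the control rates, so their absence from the text is no fault. Single power values are also too precise, since 64 may be a worst case; hence the ranges.

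Finally, these are pilot studies. That lowers the weight. However, the protocol itself claims 80% power and tests efficacy at 0.05, so its sizes should agree with that claim.

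**Conclusion.** The point holds conditionally. If 105 is the combined total, at least one separately tested study has fewer than 64, and the 80% power statement is not supported for it. That is the more natural reading, because 105 directly follows the announcement of two studies, but the documents do not confirm it. If 105 is per study, power is about 95% on the exact anchor and nothing is short.

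On the total reading, a study of 41 has about 61% power, or about 61% to 78% if 64 is the worst case over control rates. Studies of 52 and 53 have about 71% to 72%, or 71% to 87%. These figures rest on 64 being correct, on equal allocation and on a constant correlation. The even split is an assumption. The worst-case ranges also assume control rates between 10% and 50%.

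The documents do not show that 64 is wrong, that both studies are underpowered, or that more people must be enrolled. Severity is minor to moderate.

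**What to change.** In the abstract and in Power Analyses (section 7c):

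1. State the number to be randomized in each study. For Study 2, count after the smartphone induction requirement of videos on at least 6 of 7 days, since randomization follows it.
2. Say whether 105 is a total or per study, and which study or studies the 64 serves.
3. Give the power for 25 points, or the difference detectable with 80% power, for each study at its own number.
4. Do not apply the 80% statement to a study with fewer than 64 unless a calculation at that study's own size supports it.

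This is rewording plus one short calculation. It needs no extra enrolment and changes no procedure or analysis. The cost is that, if 105 is the total, the stated power will probably be less favourable for at least one study.
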